3.3 Rationale of dose/regimen, duration of treatment

The dose regimen has been selected based on the efficacy and safety results of the adult Phase III studies with the aim to yield systemic exposure comparable to that obtained in MS adult patients at the 0.5 mg dose. Based on the adult Phase III PK/PD data, it was shown that exposure levels were the best predictor of efficacy (i.e., reduction in ARR).

Clinical experience with fingolimod in a pediatric population comes from a single dose study in renal transplant patients 11-16 years of age. Administration of a single oral dose of fingolimod scaled for body weight yielded comparable total exposure to fingolimod and fingolimod-P in this group of children/adolescents versus adults receiving a fixed dose of 5.0 mg. As expected from previous clinical experience, pharmacodynamic responses to fingolimod, i.e., reduction in lymphocyte counts and in heart rate, were comparable in children/adolescents and adults.

It is known that cytochrome P450 (CYP450) activity, in children/adolescents aged 10-18 years, is comparable to that of adults (Kearns et al 2003). The relationship between body weight and elimination clearance of fingolimod-P has been investigated by integrating the evidence from two different and independent sources: a single dose PK study in renal transplant patients 11-16 years of age; an analysis of the pooled steady state concentrations from two Phase II and two Phase III studies in adult MS patients with relapsing MS. This analysis indicates that an allometric scaling method based on normalized body weight with an exponent of 0.53 is adequate to describe the relationship between body weight and elimination clearance of fingolimod-P. Using this method, fingolimod-P concentrations as a function of patient weight and dose were simulated and compared to the observed fingolimod-P concentrations from the Phase II/III studies in adult MS patients. The dose regimen yielding systemic exposure comparable to that obtained in MS adult patients was then selected.

Therefore the dose regimen chosen in this study, based on body weight, is:

- 0.5 mg/day for all patients weighing more than 40 kg (at treatment initiation and/or during the study);
- 0.25 mg/day for all patients weighing 40 kg or less. This dose may be increased based on the results of the Month 1 online pharmacokinetic analysis or if the patient has a sustained bodyweight increase to above 40 kg during the study (sustained over at least 2 visits 3 months apart).

This approach is expected to provide exposures considered safe and effective based on data available in adults. The majority of the study population, aged 10 to less than 18 years, is expected to have a bodyweight of at least 30 kg. Children below 20 kg are nonexistent in this age range, children below 25 kg occur with a 5% frequency at an age of 10 years.

All patients weighing 40 kg or less at start of Core and/or Extension Phase will have blood sampling for PK analysis conducted at Month 1 Core Phase and/or Month 1 Extension Phase, respectively. For patients treated with fingolimod, the Month 1 Core Phase and/or Month 1 Extension Phase pharmacokinetic samples will be analyzed as soon as possible (online analysis) to ensure the systemic exposure is adequate (see Section 6.7, online pharmacokinetics, for details). If the systemic exposure is below 65% of the target exposure, the dose for the individual patient will be increased to 0.5 mg at the Month 2 Core Phase and/or Month 2 Extension Phase visits via the Interactive Voice Response system (IVR system). This rapid turnover of the results and fast implementation of a dose adjustment will limit the period of potential under-exposure for the fingolimod-treated patient.

At the Month 2 Core Phase and/or Month 2 of the Extension Phase visit, all patients in the ≤ 40 kg group will again undergo the first dose monitoring procedure described in Section 3.1 and in Appendix 2.

Patients weighing 40 kg or less who have an increase in body weight over 40 kg, sustained over at least two visits, 3 months apart, will again undergo the first dose monitoring procedure described in Section 3.1 and in Appendix 2.

The flexible treatment duration of up to 24 months for the Core Phase has been chosen to allow for sufficient time to adequately assess the effects on disease activity, as measured by relapses and brain MRI, and to determine the safety and tolerability profile of chronic treatment in the pediatric MS population.

The treatment duration of 60 months (five years) for the Extension Phase is a regulatory requirement and was chosen to allow for adequate time to assess long-term safety, tolerability and look at efficacy parameters in patients treated with fingolimod.

3.4 Rationale for choice of comparator

The use of placebo as a control in the Core Phase of an agent already demonstrated to be effective in adults is for ethical reasons not deemed acceptable in the pediatric MS population (Ghezzi et al 2010, Banwell and Triplett 2005).

[figure not shown]
IFN β -1a once-weekly i.m. is the active comparator selected for the pediatric study. In the EU, it is approved for use in patients 12 years and older and is also used in younger patients in the absence of an approved treatment. Compared to the other two available IFN β agents, it is associated with less frequent injections, fewer injection site reactions and thus less burden for the patients. Furthermore, IFN β -1a was the active comparator included in the adult fingolimod Phase III program. Use of the same active comparator as in the adult program will allow for comparison of safety and efficacy outcomes in the pediatric population to those in the adults.

3.5 Purpose and timing of interim analyses/design adaptations

Interim analyses for the Data Monitoring Committee (DMC) may be performed (see Section 7.4).

A BSSR will be conducted during the study to provide estimation on ARR and the between-patient variability. The study shall maintain the required power of 80% to detect a 50%

relative treatment effect on the annualized relapse rate (two-sided 5% alpha-level). Accordingly, Novartis proposes to change the trial design from a fixed 2-year study to an information-based flexible duration design study with study duration of up to 2 years:

4 Population

Core Phase:

Male and female patients with multiple sclerosis (MS) aged 10 to less than 18 years will be included in this Core Phase study.

Patients will be recruited into two cohorts based on their puberty status (pre-pubertal, pubertal). The study will be conducted in centers worldwide. Approximately 190 patients will be randomized to receive either fingolimod or IFN β -1a. The maximum treatment duration in the Core Phase will not exceed approximately 2 years. There is no minimum duration for participation in the Core Phase.

Fingolimod Extension Phase:

The population of the Extension Phase will consist of patients who complete the double-blind treatment period on or off of study drug and meet the in/exclusion criteria for enrollment in the Extension Phase. If the study is stopped early then all patients that are enrolled in the Core Phase and that complete the EOS-CP visit will be considered to have completed the Core Phase of the study (see [Section 9.6](#)).

- Patients who complete the Core Phase on study drug will be allowed to enter the Extension Phase without any further criteria.
- Patients who complete the Core Phase but prematurely discontinued study drug during the Core Phase for any reason will be assessed for eligibility in the Extension Phase based on the exclusion criteria.

4.1 Inclusion criteria

Core Phase:

Patients eligible for inclusion in this study have to fulfill all of the following criteria:

1. Written informed consent must be obtained before any assessment is performed.

2. Male and female patients aged 10-17 years old*, inclusive (i.e., have not yet had their 18th birthday) at randomization.
3. A diagnosis of MS as defined by the revised consensus definition for pediatric MS, ([Krupp et al 2013](#), [Polman et al 2011](#)).
4. Central review of the diagnosis of pediatric MS will be required for all patients prior to randomization.
5. At least one MS relapse/attack during the previous year or two MS relapses in the previous two years prior to screening or evidence of one or more Gd enhancing lesions on MRI within 6 months prior to randomization (including screening MRI).
6. Expanded Disability Status Scale (EDSS) score of 0 to 5.5, inclusive.

*Exception: If, in a specific country, use of interferon- β -1a IM in children below a certain age is included in the Contraindications section of Avonex (interferon- β -1a IM) local product information, inclusion of such patients is not permitted in that country. E.g. the Russian Avonex product information lists use in children below the age of 12 years as a contraindication.

Fingolimod Extension Phase:

Criterion applies to all patients entering the Extension Phase.

1. Patients that originally met Core Phase Inclusion criteria and completed the Core phase on or off of study drug.

4.2 Exclusion criteria

Core Phase:

Patients fulfilling any of the following criteria are not eligible for inclusion in this study:

1. Patients with progressive MS.
2. Patients with an active, chronic disease (or stable but treated with immune therapy) of the immune system other than MS (e.g. Sjögren's disease, systemic lupus erythematosus) or with a known immunodeficiency syndrome (AIDS, hereditary immune deficiency, drug induced immune deficiency) or tested positive for HIV at Screening.
3. Patients with widespread and symmetric white matter alterations in the Screening MRI suggestive of other demyelinating disorders (e.g. metabolic disorders, mitochondrial disorders).
4. Patients meeting the definition of ADEM ([Krupp et al. 2013](#)); patients meeting criteria for neuromyelitis optica ([Wingerchuk et al 2006](#)) or tested positive for aquaporin 4 (AQP4) at Screening.
5. Patients treated with:
 - Systemic corticosteroids or adrenocorticotrophic hormone (ACTH) in the 30 days prior to Screening MRI scan
 - High dose intravenous immunoglobulin within 2 months prior to randomization
 - Natalizumab within 3 months or teriflunomide within 3 ½ months prior to randomization

- Immunosuppressive/immunomodulatory medications such as, azathioprine, methotrexate, laquinimod, ofatumumab, ocrelizumab within 6 months prior to randomization.
 - Alemtuzumab, cladribine, cyclophosphamide, mitoxantrone or rituximab at any time
 - Fingolimod at any time
 - The following antiarrhythmic drugs at Screening: Class Ia (e.g. quinidine, disopyramide) or Class III (e.g. amiodarone, sotalol) anti-arrhythmics
 - Concurrently treated with heart-rate-lowering drugs at Screening e.g.: Beta blockers, heart-rate lowering calcium channel blockers (e.g. verapamil, diltiazem or ivabradine), digoxin, anticholinesteratic agents, pilocarpine. Advice from a cardiologist should be sought regarding the switch to non-heart-rate lowering medicinal products.
6. Patients diagnosed with macular edema during the pre-randomization phase
 7. Patients with active systemic bacterial, viral or fungal infections, including tuberculosis.
 8. Patients without acceptable evidence of immunity to varicella-zoster virus, mumps, measles, rubella, diphtheria, tetanus and pertussis at Randomization (See [Appendix 3 Guidance on vaccinations](#) for guidance on acceptable evidence of immunity and requirements for serologic testing).
 9. Patients who have received any live or live attenuated vaccines (including for varicella-zoster virus or measles) within one month prior to randomization.
 10. Patients with a history or presence of malignancy.
 11. Patients with any medically unstable condition, as assessed by the investigator.
 12. Patients with any severe cardiac disease or significant findings on the screening ECG, such as:
 - History of symptomatic bradycardia or recurrent syncope
 - Known ischaemic heart disease
 - History of congenital heart disease (except conditions such as small patent ductus arteriosus, atrial septal defect, ventricular septal defect, or an ECG or rhythm abnormality, which have been assessed by a pediatric cardiologist and considered to be clinically insignificant).
 - Cerebrovascular disease
 - History of myocardial infarction
 - Congestive heart failure
 - History of cardiac arrest
 - Uncontrolled hypertension despite prescribed medications
 - Resting (sitting) heart rate <55 bpm (in patients 12 years or older) and <60 bpm (in patients below 12 years)
 - Severe untreated sleep apnea
 - Sick sinus syndrome or sino-atrial heart block
 - QTcF interval >450 msec in males and >460 msec in females or relevant risk factors for QT prolongation (e.g. hypokalaemia, hypomagnesemia, congenital QT

prolongation) or treatment with QT prolonging drugs with a known risk of Torsades de pointes (e.g. citalopram, chlorpromazine, haloperidol, methadone, erythromycin) or history of familial long QT syndrome or known family history of Torsades de Pointes.

- Second degree Mobitz type II or higher AV block
13. Patients with any pulmonary conditions, as determined by the investigator, including severe asthma defined as per the 2010 WHO uniform definition on severe asthma ([Bousquet et al 2010](#)).
 14. Positive results of screening period testing for serological markers for hepatitis A, B, C and E indicating acute or chronic infection:
 - anti-HAV IgM
 - HBs Ag and/or anti-HBc IgM
 - anti-HCV IgG or HCV-RNA PCR
 - anti- HEV IgM or IgG (if positive IgG: do HEV-RNA PCR: if negative, patient can be included)
 15. Patients with any of the following hepatic conditions:
 - Chronic liver or biliary disease, acute or chronic pancreatitis, with the exception of Gilbert's syndrome;
 - Liver enzymes
 - ALT, AST, alkaline phosphatase, GGT, >2 x upper limit of normal (ULN) range for age (for pre-pubertal patients > 1 X ULN or > 2 X ULN if currently treated with IFN or glatiramer acetate). Elevations of alkaline phosphatase should not be used in isolation to exclude subjects, and would require Investigator discretion.
 - Bilirubin elevations not in the context of Gilberts Syndrome: Total and conjugated bilirubin >1.5 X ULN (for pre-pubertal patients >1 X ULN or > 1.5 X ULN if currently treated with IFN or glatiramer acetate).
 16. Patients with severe renal insufficiency (GFR <30 ml/min/1.73 m²).
 17. Patients with lymphocyte count < 800 cells (mm³).
 18. Patients with any of the following neurologic/psychiatric disorder:
 - History of any type of epileptic seizure(s) as well as psychogenic non-epileptic seizure(s) during the past 12 months before screening;
 - History of substance abuse (drug or alcohol) or any other factor (i.e., serious psychiatric condition) that may interfere with the subject's ability to cooperate and comply with the study procedures;
 - Progressive neurological disorder, other than MS, which may affect participation in the study or require the use of medications not allowed by the protocol
 19. Patients unable to undergo MRI scans, including claustrophobia or history of hypersensitivity to gadolinium-DTPA.
 20. Pregnant or nursing females, where pregnancy is defined as the state of a female after conception and until the termination of gestation, confirmed by a positive HCG laboratory test.

21. Female patients of childbearing potential, defined as all females physiologically capable of becoming pregnant, unless they agree to abstinence or, if sexually active, the use of contraception as defined in [Section 6.6](#).
22. History of hypersensitivity to any of the study drugs or to drugs of similar chemical classes.
23. Patients with a score of “yes” on item 4 or 5 of the Suicidal Ideation section of the C-SSRS, if this ideation occurred in the past 6 months, or with a score of “yes” on any item of the Suicidal Behavior section, except for “Non-Suicidal Self Injurious Behavior”, if this behavior occurred in the past 2 years.
24. Patients who have received an investigational drug or therapy within 180 days or 5 half-lives of randomization, whichever is longer.

No additional exclusions may be applied by the investigator, in order to ensure that the study population will be representative of all eligible patients.

Fingolimod Extension Phase:

Criteria apply to patients who completed the Core Phase, but prematurely discontinued study drug.

1. Premature discontinuation of the study drug during the Core Phase due to:
 - an adverse event,
 - serious adverse event,
 - laboratory abnormality
 - other conditions leading to permanent study drug discontinuation due to safety reasons as described in protocol [Section 5.5.9](#).

Note: If a patient was discontinued due to lack of efficacy in the Core Phase, the patient may be offered the option to enter the extension trial if the investigator determines it is in the patient’s best interest when considering all available treatment options.

2. Patients with known new events or concomitant medications (washout periods required prior to Visit 15) that would exclude them from the Core Phase exclusion criteria. Serological or other additional tests will not be required.

5 Treatment

5.1 Investigational and control treatment

Investigational drug: Core Phase and Fingolimod Extension Phase

Two dose-strengths will be used (depending on the patients’ body weight) with the aim to achieve systemic exposure in the pediatric population that is comparable to that obtained in MS adult patients at the 0.5 mg dose:

- Fingolimod 0.5 mg capsule, administration orally once daily in patients weighing more than 40 kg

- Fingolimod 0.25 mg capsule, administration orally once daily in patients weighing 40 kg or less (patients weighing ≤ 40 kg at the start of the Extension Phase will receive the 0.5 mg/d dose if they had a dose increase at Month 2 during the Core Phase)

Dose adjustments to ensure exposure is appropriate may be implemented in patients with a body weight 40 kg or less based on online PK assessment (see [Section 3.3](#)). During the course of the study any patient receiving the lower fingolimod dose of 0.25 mg who reaches the weight of more than 40 kg (sustained over at least 2 visits, 3 months apart), will be automatically switched to the 0.5 mg dose strength. Dose adjustments for any other reason are not permitted. Patients in the IFN β -1a arm whose bodyweight increases to above 40 kg during the Core Phase (sustained over at least 2 visits, 3 months apart), will have a sham increase in their oral dose. The dose increases will be done in a blinded fashion (refer to [Section 3.3](#)).

Oral study drug may be taken with or without food, preferably at the same time every day.

Study medication will be dispensed at the randomization visit (Day 1).

Control treatment: Core Phase

Interferon β -1a (Avonex[®]), administration intramuscular (i.m.) injection once weekly

The first dose of IFN β -1a i.m. at Day 1 will be administered intramuscularly at the site by the First Dose Administrator or nurse. Site personnel will provide training to the patients and their parents/caregivers on the correct procedure for administration of i.m. injections. A patient leaflet and/or oral instructions will be provided. The patient leaflet and/or oral instructions describe information related to the i.m. study drug including storage information, precautions and instructions for administering i.m. injections. This information should be reviewed with the patient and his/her parents/caregivers to ensure that they understand the correct procedure.

Injectable study drug may be initiated at $\frac{1}{4}$ or $\frac{1}{2}$ volume per clinical practice at the individual sites. Full dose should, however, be achieved by the fourth week of injections. Prophylaxis and treatment of flu-like symptoms with e.g. paracetamol/acetaminophen may be performed per clinical practice at the site.

Matching placebo capsules and syringes: Core Phase

- Matching fingolimod placebo capsules for oral administration once daily.
- Matching IFN β -1a placebo in pre-filled syringes for i.m. injection once weekly.

The fingolimod capsules (0.25 mg and 0.5 mg) and matching placebo capsules will be identical in appearance and will be packed in identical bottles. Both, the IFN β -1a and its matching placebo will be packed and supplied in pre-filled syringes.

5.2 Treatment arms

Core Phase:

Randomized patients will be assigned to fingolimod + matching IFN placebo injection or IFN β -1a injection + matching fingolimod placebo capsule in a ratio of 1:1.

Fingolimod Extension Phase:

All patients will receive fingolimod in the Extension Phase.

5.3 Treatment assignment

Core Phase:

At Visit 3, all eligible patients will be randomized via Interactive Voice Response (IVR) system to one of the two treatment arms. The investigator or his/her delegate will contact the IVR system after confirming that the patient fulfills all the inclusion/exclusion criteria. The IVR system will assign a randomization number to the patient, which will be used to link the patient to a treatment arm and will specify a unique medication number for the first package of study drug to be dispensed to the patient. The randomization number will not be communicated to the caller.

Fingolimod Extension Phase:

At Visit 15 (first Extension Phase visit), all eligible patients will be assigned via Interactive Voice Response (IVR) system to receive either 0.25 mg/d or 0.5 mg/d fingolimod.

Patients randomized in the Core Phase to receive fingolimod will continue to receive the same dose of fingolimod that they were receiving at Visit 14 / EOS-CP (End of Core Phase treatment) Note: A dose increase at Visit 15 is possible if the patient had a sustained increase in weight to >40 kg at two consecutive visits at least three months apart.

Patients randomized to receive interferon- β -1a during the Core Phase of the study will be assigned to receive fingolimod (0.5 or 0.25 mg/d based on body weight as described in [Section 5.1](#). Note: The body weight of a patient must be sustained at >40 kg at two consecutive visits at least three months apart for a patient to receive the 0.5 mg/d dose of fingolimod at the start of the Extension Phase.

The randomization numbers for the Core Phase will be generated using the following procedure to ensure that treatment assignment is unbiased. A patient randomization list will be produced by the IVR system provider using a validated system that automates the random assignment of patient numbers to randomization numbers. These randomization numbers are linked to the different treatment arms, which in turn are linked to medication numbers. A separate medication list will be produced by or under the responsibility of Novartis Drug Supply Management using a validated system that automates the random assignment of medication numbers to study drug packs containing each of the study drugs.

Randomization will be stratified by region, due to the anticipated low number of patients that will be enrolled at each site, and by puberty status (pre-pubertal and pubertal).

The randomization scheme for patients will be reviewed and approved by a member of the Biostatistics Quality Assurance Group.

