Patients who prematurely discontinue study drug and remain in the study will be followed in an abbreviated schedule of assessments for the duration of the double-blind treatment period. Upon discontinuation of the study drug, patients must complete the Visit 14 end of study phase (EOS-CP) visit as soon as possible, followed by a 3-month follow-up visit, before continuing in the abbreviated schedule of assessments.

Patients who complete the double-blind treatment phase (on or off study drug) may be eligible to enter a long-term Extension Phase to receive treatment with fingolimod. Patients who complete the double-blind treatment period on study drug, but do not enter the Extension Phase will return for a follow-up visit 3 months after the Visit 14- EOS-CP visit.

Fingolimod Extension Phase:

The Extension Phase is a 60-month (5 year) study phase for eligible patients who complete the Core Phase of the study and meet all inclusion/exclusion criteria. All patients will be treated with fingolimod (either 0.5 mg/d or 0.25 mg/d based on body weight). To comply with local requirements if, in a specific country/site the Extension Phase is not allowed by the Health Authority/IRB then that country/site will not be required to participate in the Extension Phase.

The Core Phase treatment will remain blinded until the Core Phase database is locked.

The first dose of study drug will be provided in the clinic at Visit 15 (the day after study completion of the Core Phase), following the first dose monitoring procedures. The first dose monitoring in the Extension Phase must be conducted by the independent first dose administration team and is required for all patients in order to maintain blinding of the Core Phase treatment.

Patients randomized in the Core Phase to receive fingolimod will continue to receive the same dose of fingolimod (A dose increase at Visit 15 is possible if the patient had a sustained increase in weight to >40 kg at two consecutive visits at least three months apart). Patients randomized to receive interferon- β -1a during the Core Phase of the study will be assigned to receive fingolimod (0.5 or 0.25 mg/d based on body weight; the body weight of a patient must be sustained at >40 kg at two consecutive visits at least three months apart for a patient to receive the 0.5 mg/d dose of fingolimod at the start of the Extension Phase).

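### Read literally, the extension dosing note starts interferon patients already above 40 kg on half dose if their core phase ends before about Month 6

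*Protocol*

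**What the plan says.** For patients randomised to interferon, Section 5.3 first says they "will be assigned to receive fingolimod (0.5 or 0.25 mg/d based on body weight as described in" Section 5.1. A note then adds the condition for starting on 0.5 mg: "The body weight of a patient must be sustained at >40 kg at two consecutive visits at least three months apart". The synopsis repeats it: "the body weight of a patient must be sustained at >40 kg at two consecutive visits at least three months apart". Neither place limits the condition to patients who were light at core entry.

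Section 5.1 covers both phases and has no two-visit condition for a patient who is already heavy enough: "Fingolimod 0.5 mg capsule, administration orally once daily in patients weighing more than 40 kg". Section 3.3 agrees: "0.5 mg/day for all patients weighing more than 40 kg (at treatment initiation and/or during the study"). The synopsis paragraph on investigational therapy says the same, and Section 3.1 sets the interferon patients' extension dose by body weight with a reference to Section 5.1.

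In Section 5.1 the sustained-weight test belongs to a different situation, a patient on the low dose who gains weight: "any patient receiving the lower fingolimod dose of 0.25 mg who reaches the weight of more than 40 kg", with the switch then automatic. The parallel note for the fingolimod arm in Section 5.3 is also about a gain: "A dose increase at Visit 15 is possible if the patient had a sustained increase in weight to >40 kg".

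Section 4 states that the core phase has no minimum duration, and that after an early stop everyone who attends the end-of-core visit counts as a completer.

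**The concern.** Section 5.3 points to Section 5.1 and then, in the next sentence, states a stricter rule. With only two strengths on offer, a patient who fails the stricter rule receives 0.25 mg. The two texts therefore give the same patient doses that differ twofold. The IVR system assigns the Visit 15 dose and can be programmed to only one of them.

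Three things are at stake.

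- **Dose.** A patient well above 40 kg could spend months on a dose meant for lighter children. Online PK correction is limited to patients of 40 kg or less, and Section 5.1 bars adjustments for any other reason, so only the sustained-weight switch would correct it.
- **Burden.** The later step up needs another monitored first-dose visit of at least six hours (Section 6.5.3). Starting on 0.5 mg avoids that.
- **Blinding.** Section 5.4 keeps the extension dose blinded only for patients of 40 kg or less at core start. That fits only if every heavier patient gets 0.5 mg. Fingolimod patients above 40 kg at core entry continue on 0.5 mg, so an openly known 0.25 mg dose in such a patient would point to interferon before core database lock. This is an inference from Section 5.4.

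**Working it through.** No power or sample-size figure is involved. The check is a visit calendar, followed by a rough exposure calculation.

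**1. When can the note first be met?** Section 3.1 puts core visits at Day 1, Week 2, Months 1, 2 and 3, then every three months. With 30-day months these fall on days 1, 14, 30, 60, 90, 180 and 270. The gaps between successive visits are 13, 16, 30, 30, 90 and 90 days. The first gap of at least 90 days is Month 3 to Month 6.

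**2. Does an end-of-core visit at the stop time help?** For cores stopped at 2, 2.9, 3, 4, 5 or 5.9 months, no successive pair is three months apart. The earliest qualifying stop is day 180, or day 170 if Month 3 falls on day 80 within its ±10-day window. If Month 3 falls on day 100, a Month 6 visit on day 180 gives only 80 days, and the first qualifying pair becomes Months 6 and 9. Visit 15 follows the end-of-core visit by at most 14 days (Section 6), so it cannot supply the gap.

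**3. Sensitivity to the word *consecutive*.** Sections 3.3 and 5.1 word the sustained-weight rule without it. Day 1 and Month 3 then qualify (89 days by study-day count, taken here as three months), and the gap shrinks to cores under about three months.

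**4. How long would a low dose last?** Extension visits are Day 1, Week 2, Months 1, 2, 3, 6, 9 and 12. Take a core stopped at Month 4 and apply the automatic switch of Section 5.1:

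| Visits counted | Successive visits required? | Time on 0.25 mg |
|---|---|---|
| Core and extension | No | None (core Day 1 and Month 3 already qualify) |
| Extension only | No | 3 months (Day 1 to Month 3) |
| Either | Yes | 6 months (Month 3 to Month 6) |

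For a two-month core, counting core visits and not requiring successive ones, the switch comes at extension Month 1.

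**5. Exposure on 0.25 mg.** Section 3.3 gives an allometric exponent of 0.53 for clearance. Exposure relative to an adult on 0.5 mg is then

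relative exposure = 0.5 × (reference weight / patient weight)^0.53.

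The documents give no adult reference weight, so 60 to 80 kg is an assumption.

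| Patient weight | Ref. 60 kg | Ref. 70 kg | Ref. 80 kg |
|---|---|---|---|
| 41 kg | 0.612 | 0.664 | 0.713 |
| 50 kg | 0.551 | 0.598 | 0.641 |
| 60 kg | 0.500 | 0.543 | 0.582 |

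Section 3.3 raises the dose of a lighter patient when exposure is below 65% of target. On this formula 0.25 mg falls below 65% above about 37, 43 and 49 kg for the three reference weights.

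**6. Who could be affected?** The Amendment 7 description of Section 9.6 has end-of-study visits by June 2017 if the information projection is sufficient. Six months back from that is about December 2016. Only interferon patients above 40 kg randomised after that date would have too short a core, and the documents do not show whether enrolment was still open then.

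**The case against.** The strongest reply is that intent is clear and no one would dose a 60 kg patient at 0.25 mg. Section 5.1 reserves the low dose for patients of 40 kg or less. Every safeguard around it (Month 1 PK, Month 2 monitoring, blinding of the extension dose) is defined for that group only. The fingolimod note speaks of an increase in weight, and SAP deviation S12, although it is a core-phase per-protocol criterion, describes weight rising above 40 kg. All of this stands, and it is why the point is a wording defect. It does not settle what an IVR programmer does with a sentence that says *must* and has no qualifier.

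Second, the Month 6 threshold depends on reading *consecutive* strictly, and the automatic switch might act at Visit 15. Both are correct. Under the looser reading only cores under about three months are caught, and the Month 4 example may involve no low-dose time. But *consecutive* is the word used in Section 5.3 and the synopsis, and the plan does not say whether core weights count toward the switch.

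Third, the number affected may be zero. It takes an early stop, late randomisation to interferon, weight above 40 kg, extension entry and literal programming. This also stands.

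Fourth, the blinding clue is weak. It arises only at Visit 15, after that patient's own end-of-core assessments, and the two core capsule strengths look identical. The exposure figures rest on an assumed reference weight, and the 65% limit was set for measured concentrations in lighter patients, so they only indicate scale.

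**Conclusion.** The point holds: the rule is wrong as written, with small practical reach. Followed literally, Section 5.3 and the synopsis withhold 0.5 mg at extension start from interferon patients above 40 kg throughout whose regular-schedule core ends before about Month 6. This contradicts Section 5.1 and does not fit Section 5.4. It should be corrected, but it does not threaten the trial's conclusions: the core primary and key secondary analysis methods are unaffected.

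The conclusion rests on the regular visit schedule and the literal word *consecutive*. A missed visit or a prolonged pre-randomisation period could supply a qualifying pair earlier. The core assessment schedule (Table 6-1) is not in the text available, so weighing at screening and baseline could not be checked. Patients of 40 kg or less at core entry, and those who stop study drug early and have the three-month follow-up visit, are outside this point.

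**What to change.** In Section 5.3 and the matching synopsis paragraph, limit the two-visit condition to interferon patients who weighed 40 kg or less at core entry. Add that interferon patients above 40 kg at core entry, and still above it, start the extension on 0.5 mg whatever the length of their core phase. Then check the IVR specification for Visit 15 against the corrected text. The cost is one sentence in two places and a specification check, with no extra visits or patients.
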